# 6.3 Rationale for Trial Design, Dose, and Endpoints

# 6.3.1 Rationale of Trial Design

In addition to assessing safety, tolerability, and PK of TAK-831, the proposed study is aimed at providing information on the relationship between concentrations of TAK-831 and to be explored in both plasma and CSF in healthy subjects in order to support dose selection for the follow-up studies planned to evaluate PD effects of TAK-831 in subjects with schizophrenia. CCI assessments will be conducted in non-CSF cohorts for exposure-response analysis of ECG parameters, or in CSF cohorts where the first CSF sample is collected through single lumbar puncture prior to the start of CCI on Day -1.

#### 6.3.2 Rationale for Dose

Based on the results of toxicology studies, the monkey is considered the more sensitive species. The NOAEL in the 13-week repeat dose study was based on adverse findings of vomiting, diarrhea, and loose stool at the top dose of 600 mg/kg/day. Therefore, the next lower dose tested, 100 mg/kg/day, was assigned the NOAEL for both sexes. This NOAEL was associated with mean  $C_{max}$  values of 1340 and 1270 ng/mL and mean  $AUC_{24}$  values of 7490 and 9190 h\*ng/mL for males and females, respectively, on Day 91.

As the adverse effects of treatment in the monkey (vomiting, diarrhea, and loose stool) are easily monitored in humans, exceeding the NOAEL of 100 mg/kg/day in monkeys may be warranted in order to achieve adequate CNS exposures in humans. The targeted maximum exposure in humans is that attained in monkeys at 600 mg/kg/day. Dose escalation will be stopped if significant vomiting or diarrhea is observed in humans. In monkeys, at 600 mg/kg/day (dosed as 300 mg/kg, BID), respective mean  $C_{max}$  and  $AUC_{24}$  values on Day 91 were 3680 ng/mL and 35,700 h\*ng/mL, sexes combined.

The highest dose tested in the MRD portion of Study TAK-831-1001 was 400 mg daily of the oral suspension formulation for 14 days. At this dose level, there were no significant adverse effects reported, and  $C_{max}$  exposures had reached those of female monkey at the NOAEL dose ( $C_{max}$  1270 ng/mL and AUC24 3454 h\*ng/mL) (Table 6.b).

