Since, the highest dose tested in single rising dose portion of Study TAK-831-1001 was 750 mg administered as a suspension, all dose levels above 750 mg/day will be tested first in SD setting before MD in subsequent cohorts.

All decisions concerning dose escalation will be made by Takeda (at a minimum, the clinical science representative[s], quantitative clinical pharmacologist, study statistician and pharmacovigilance physician) and the principal investigator. The investigator and subjects will remain blinded throughout the study, but at the completion of each cohort, specific Takeda personnel listed in associated study documentation may be unblinded to analyze data considered necessary to determine subsequent doses and cohort management decisions. All data presentations prepared for discussions with the investigator and site staff will contain only blinded study data, except in the event that formal study unblinding procedures detailed in Protocol Section 8.1.5 have been followed and discussion of related data is required.

If agreement regarding a dose escalation decision cannot be reached between the principal investigator and Takeda, the study will be stopped.

Based on emerging safety and tolerability and PK data, the planned dose levels may be modified.

All adverse events reported during the Treatment Period, both within and across cohorts, up to the time of discharge will be evaluated to assess the need for subject and/or study termination in accordance with the prespecified criteria for discontinuation/termination (Section 6.5).

Following assessment of the adverse event data and predefined criteria for study termination, dose escalation may be interrupted/stopped if these criteria are met. Based on review of study data as outlined above, Takeda, in consultation with the principal investigator, will decide if and how it is appropriate for the study to proceed.

Dose escalation may be interrupted/stopped if:

- Exposures in any cohort exceed those observed at the top dose tested in the monkey toxicity study, that is, a mean  $C_{max}$  of 3680 ng/mL or a mean  $AUC_{24}$  of 35,700 hr\*ng/mL.
- The exposures reach the plasma exposure plateau in the 2 highest dose cohorts.
- One or more subjects in any single cohort or across more than 1 cohort experience an SAE or 2 severe or clinically significant AEs occur that are considered related to study drug.

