**Table 6.b Exposure Margins** 

	Dose	C max	AUC 24	Margin (a)	
Species-Study	(mg/kg/day or mg)	(ng/mL)	(h*ng/mL)	$C_{max}$	AUC 24
Rat 13-week	1000	11,000 (M)	162,000 (M)	8.7 (M)	46.9 (M)
(Day 91)	(NOAEL)	26,100 (F)	355,000 (F)	20.6 (F)	102.8 (F)
Monkey 13-week	100 (50 BID)	1340 (M)	7490 (M)	1 (M)	2.2 (M)
(Day 91)	(NOAEL)	1270 (F)	9190 (F)	1 (F)	2.7 (F)
	600 (300 BID)	4650 (M)	45,500 (M)	3.7 (M)	13.2 (M)
	(vomiting, diarrhea)	2710 (F)	25,900 (F)	2.1 (F)	7.5 (F)
Human MRD (Day 14)	400 mg QD (suspension form)	1270 (M)	3454 (M)	-	-

F=female, M=male.

Based on these data, the proposed doses in the current study are as follows:

Cohort 1 subjects will receive a starting dose of TAK-831 600 mg QD as a T2 tablet formulation, which is expected to achieve geometric mean TAK-831  $C_{max}$  and  $AUC_{24}$  about 60% and 83%, respectively of that of 400 mg suspension formulation under fasted conditions.

In parallel to Cohort 1, Cohort 2 will test the suspension formulation with 800 mg dose. Subsequent cohorts will have dose escalated as tolerable. Dose escalation will be stopped according to the stopping rules detailed in Section 6.2.

Proposed dose levels as well as dosing intervals for the subsequent cohorts may be adjusted after reviewing safety, tolerability, PK, and/or PD data of Cohorts 1 and 2.

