# 6.5.5 Criteria for Premature Termination or Suspension of the Trial

#### 6.5.5.1 Criteria for Premature Termination or Suspension of Trial

The study will be completed as planned unless 1 or more of the following criteria are satisfied that require temporary suspension or early termination of the study.

- New information or other evaluation regarding the safety or efficacy of the study medication that indicates a change in the known risk/benefit profile for the compound, such that the risk is no longer acceptable for subjects participating in the study.
- Significant violation of Good Clinical Practice (GCP) that compromises the ability to achieve the primary study objectives or compromises subject safety.
- Meeting study-specific criteria for terminating the study (eg, study meets predefined rule for futility or benefit, study meets predefined stopping rules within or between cohorts per Section 6.2).
- Two or more subjects in any single cohort or across more than 1 cohort experience alanine aminotransferase (ALT) and/or aspartate aminotransferase (AST) elevations >5 times the upper limit of normal (ULN) in the absence of a concomitant bilirubin increase (see point 3 below)\*. If 2 subjects in 1 dose level after dosing show the following findings in 2 consecutive measurements within 24 hours:

- ALT or AST  $\ge 3 \times ULN$ , or
- ALT or AST  $\ge 2 \times ULN$  and ALT or AST  $\ge 5 \times baseline$  value, or
- Total bilirubin  $\ge 2 \times ULN$  or
- International normalized ratio (INR) >1.5 or
- ALT and/or AST elevations >3×ULN with the appearance of fatigue, nausea, vomiting, right upper quadrant pain or tenderness, fever, rash and/or eosinophilia (>5%) without findings of cholestasis or other alternate etiology to explain the elevations (ie, "Hy's Law cases").

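### The two-week ALT/AST limb in Section 7.5 cannot in practice act during planned dosing, and the GI stop in Section 6.3.2 is missing from the Section 6.2 stopping list

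*Protocol*

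**What the plan says.** **Liver rule.** Protocol Section 7.5, item 1a, requires study drug to be stopped at once if any of four conditions arises during treatment:
- ALT or AST above 8×ULN;
- ALT or AST above 5×ULN lasting more than two weeks;
- ALT or AST above 3×ULN with raised bilirubin or INR;
- ALT or AST above 3×ULN with listed symptoms, rash or eosinophilia.

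Section 2.0 puts dosing on Day 1 and Days 3 to 16. Section 3.0, footnotes (a) and (l), puts the safety laboratory tests at Screening, Check-in, Day 1 predose, Day 10 predose and study exit, which is Day 17 (non-CSF) or Day 19 (CSF). Section 7.2, item 21, excludes ALT or AST above 1.5×ULN at entry.

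The study-level liver criteria in Section 6.5.5.1 need two subjects. One is two or more subjects above 5×ULN. The other begins "If 2 subjects in 1 dose level after dosing show the following findings in 2 consecutive measurements within 24 hours".

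**GI rule.** Section 6.3.2 explains that vomiting, diarrhea and loose stool set the monkey NOAEL, and that the trial may exceed it because these effects are easy to monitor. It sets the ceiling: "The targeted maximum exposure in humans is that attained in monkeys at 600 mg/kg/day". It also states: "Dose escalation will be stopped if significant vomiting or diarrhea is observed in humans". After Table 6.b the same section adds: "Dose escalation will be stopped according to the stopping rules detailed in Section 6.2".

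Section 6.2 uses the words "dose escalation may be interrupted/stopped if". Its list covers the exposure limits, an exposure plateau, related psychiatric symptoms or suicidal ideation, and a general adverse-event trigger in which one or more subjects "experience an SAE or 2 severe or clinically significant AEs occur that are considered related to study drug". It does not name vomiting or diarrhea.

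**The concern.** A stopping rule protects subjects only if it can be met while there is still drug to stop, and if the people applying it find it where they are told to look.

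The two-week limb appears to fail the first test. The persistence it asks for is about as long as the whole treatment period, and the laboratory schedule could not document it in time. What is at stake is continued dosing in a healthy volunteer with a marked, isolated transaminase rise.

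The GI stop appears to fail the second. It sits beside the argument for exceeding the NOAEL, while the list named as the stopping rules leaves it out. What is at stake is whether the escalation team would treat one significant non-serious case as a stop.

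The two points share no mechanism and need separate fixes.

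**Working it through.** **A. The ALT/AST limb**

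The planned duration reproduces: Days 3 to 16 inclusive = 16 − 3 + 1 = 14 multiple-dose days, as the Study Summary states. With Day 1 there are 15 dosing days.

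1. *Scheduled tests.* Postdose tests are 17 − 10 = 7 days apart (non-CSF) or 19 − 10 = 9 days apart (CSF). The limb needs more than 14 days.
2. *Pairs that include the Day 1 predose sample.* Day 1 to Day 17 is 16 days and Day 1 to Day 19 is 18 days. Both end after the last dose, and both would need a value above 5×ULN before any drug, in a subject admitted at no more than 1.5×ULN.
3. *A Day 10 finding.* More than 14 days after Day 10 is first reached on Day 10 + 15 = Day 25, which is 25 − 16 = 9 days after the last dose.
4. *Best case, with unlimited unscheduled testing.* Day 1 dose to Day 16 dose = 15 × 24 = 360 h. Two weeks = 14 × 24 = 336 h. The difference is 360 − 336 = 24 h. Only a rise above 5×ULN within 24 hours of the Day 1 dose could last more than 14 days before the last dose, and no postdose liver test is scheduled then. Because the Day 15 dose falls exactly 336 h after the Day 1 dose, such a case could withhold only the Day 16 dose.
5. *What is left uncovered.* The other three limbs cover values above 8×ULN, and values above 3×ULN with bilirubin, INR or clinical features. The study-level criteria need two subjects. One subject with an isolated, asymptomatic value above 5 and up to 8×ULN falls outside all of these.
6. *Dosing that remains after Day 10.* Days 11 to 16 = 6 of 15 dosing days (40%) if the Day 10 dose has been given. Days 10 to 16 = 7 of 15 (47%) if the result is back first.

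**B. The GI stop**

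Set side by side, reading 'significant' in Section 6.3.2 as severe or clinically significant:

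| Case | Section 6.3.2 | Section 6.2 list |
|---|---|---|
| One non-serious significant GI event | Stop | No trigger |
| Two such events, not judged related | Stop | No trigger |
| Two related events | Stop | Trigger, worded 'may' |
| One related serious GI event | Stop | Trigger, worded 'may' |

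The sections differ on whether a trigger exists only in the first two rows. In the last two they differ only in the verb.

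The exposure figures give the context. The ceiling reproduces from Table 6.b as the mean of the sexes at 600 mg/kg/day: (4650 + 2710)/2 = 3680 ng/mL for Cmax and (45,500 + 25,900)/2 = 35,700 h*ng/mL for AUC24. Against the NOAEL:
- Cmax: 3680/1340 = 2.75 (male) and 3680/1270 = 2.90 (female);
- AUC24: 35,700/7490 = 4.77 (male) and 35,700/9190 = 3.88 (female).

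These ratios show why GI events matter here. They do not measure the effect of the wording mismatch.

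**The case against.** **On the liver limb.** The limb is inert, not harmful: it does not authorize continued dosing. Several discretionary routes remain:
- Section 7.5, item 1, allows withdrawal for any adverse event that poses an unacceptable risk.
- Section 7.6 lets the investigator discontinue a subject by reference to the Section 6.5.5 criteria.
- The footnote to Section 6.5.5.1 allows the study to stop after one subject.
- Section 9.0 allows unscheduled tests, and subjects are confined throughout dosing.
- Section 10.2.8.5 requires an adverse-event record and a liver-test form after two consecutive values above 3×ULN.
- Section 6.4 permits longer dosing, under which the limb could act.

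All of this stands, and it rules out the stronger inference that a subject at 5 to 8×ULN is unprotected or must continue. It does not make the limb work on the planned schedule. Section 7.5 sets out a mandatory stop, and discretion is a different thing.

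**On the GI stop.** A reader might infer that the protocol contradicts itself or has no usable GI stop. The documents do not support that. Section 6.3.2 is itself operative protocol text. The permissive wording in Section 6.2 never prevents obeying it, and the general adverse-event trigger already catches two related GI events, even in one subject. Section 6.2 also requires all adverse events in the treatment period to be evaluated, and the study stops if sponsor and investigator cannot agree on escalation.

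In the current Table 6.a, Cohorts 4 and 5 are at 100 mg and 15 mg. Upward escalation beyond Cohort 2 therefore rests on cohorts whose dose is undetermined (Cohort 6) or not legible in the text available (Cohort 3).

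A reader might also see a clash with Section 6.5.5.1, which speaks of "criteria are satisfied that require temporary suspension or early termination of the study" and gives as an example that the "study meets predefined stopping rules within or between cohorts per Section 6.2". But that section concerns suspending or ending the trial and Section 6.2 concerns escalation. Different actions can carry different verbs.

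**Conclusion.** Both points hold as separate defects of wording, and the liver point is the stronger.

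**Liver.** One of the four numeric drug-stopping limbs in Section 7.5 is in effect inoperative on the planned schedule. The gap is one subject with isolated, asymptomatic ALT or AST above 5 and up to 8×ULN. If this is found on Day 10, 6 or 7 of 15 dosing days (40% or 47%) remain with no automatic stop. This assumes the planned dosing days and laboratory schedule, and entry values within the exclusion limit. The documents give no rate for such elevations, so no probability is attached.

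**GI.** The mandatory stop in Section 6.3.2 is missing from the list that the same section names as the stopping rules. This is an inconsistency. It changes whether a trigger exists only for a single significant non-serious event, or for events not judged related. No GI rate is stated, so the size cannot be put as a probability either.

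Neither point affects an endpoint or an analysis. Both concern subject protection and are worth correcting.

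**What to change.** **Section 7.5, item 1a.** Replace the two-week limb with: *ALT or AST >5×ULN confirmed on prompt repeat*. The cost is an occasional unscheduled repeat liver test and an earlier stop for some subjects whose values might have settled. No scheduled visit or draw is added.

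**Section 6.2.** Add a bullet that keeps the mandatory verb, for example: *Dose escalation will be stopped if any subject has vomiting or diarrhea that is severe (Section 10.2.1) or judged clinically significant*. Have Section 6.3.2 refer to it. This supplies the grade and the number of subjects that Section 6.3.2 leaves open. The cost is that one case, related or not, stops escalation, as a literal reading of Section 6.3.2 already requires. If the sponsor wants a relatedness condition or a higher count, both sections should say so.

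Section 6.5.5.1 needs no change.

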**Table 6.b Exposure Margins** 

	Dose	C max	AUC 24	Margin (a)	
Species-Study	(mg/kg/day or mg)	(ng/mL)	(h*ng/mL)	$C_{max}$	AUC 24
Rat 13-week	1000	11,000 (M)	162,000 (M)	8.7 (M)	46.9 (M)
(Day 91)	(NOAEL)	26,100 (F)	355,000 (F)	20.6 (F)	102.8 (F)
Monkey 13-week	100 (50 BID)	1340 (M)	7490 (M)	1 (M)	2.2 (M)
(Day 91)	(NOAEL)	1270 (F)	9190 (F)	1 (F)	2.7 (F)
	600 (300 BID)	4650 (M)	45,500 (M)	3.7 (M)	13.2 (M)
	(vomiting, diarrhea)	2710 (F)	25,900 (F)	2.1 (F)	7.5 (F)
Human MRD (Day 14)	400 mg QD (suspension form)	1270 (M)	3454 (M)	-	-

F=female, M=male.

Based on these data, the proposed doses in the current study are as follows:

Cohort 1 subjects will receive a starting dose of TAK-831 600 mg QD as a T2 tablet formulation, which is expected to achieve geometric mean TAK-831  $C_{max}$  and  $AUC_{24}$  about 60% and 83%, respectively of that of 400 mg suspension formulation under fasted conditions.

In parallel to Cohort 1, Cohort 2 will test the suspension formulation with 800 mg dose. Subsequent cohorts will have dose escalated as tolerable. Dose escalation will be stopped according to the stopping rules detailed in Section 6.2.

Proposed dose levels as well as dosing intervals for the subsequent cohorts may be adjusted after reviewing safety, tolerability, PK, and/or PD data of Cohorts 1 and 2.

# **6.3.3** Rationale for Endpoints

#### 6.3.3.1 Primary Endpoint

The primary endpoint for this trial is the composite of safety variables to determine the safety and tolerability of oral multiple doses of TAK-831, and dose-limiting effects of TAK-831 and are common for this type of study.

# 6.3.3.2 Secondary Endpoint

The secondary endpoints consist of standard plasma PK variables to determine drug exposure at each dose to facilitate dose escalation.

# 6.3.3.3 Exploratory Endpoints

a) Margins relative to Day 14 exposures in humans administered 400 mg/day.

# 6.3.4 Critical Procedures Based on Trial Objectives: Timing of Procedures

For this trial, collecting safety data and collecting blood in all cohorts and CSF samples in one or more cohorts for TAK-831 PK and PD are the critical procedures.

- At any postdose time point, safety data need should be collected as close to the exact time point as possible.
- At any postdose time point, the blood and/or CSF sample for TAK-831 PK, and PD needs to be collected as close to the exact time point as possible.
- All other procedures should be completed as close as possible, either before or after the prescribed/scheduled time.
- The order of priority can be changed during the trial with joint agreement of the investigator and the sponsor.

Any nonscheduled procedures required for urgent evaluation of safety concerns take precedence over all routine scheduled procedures.

# 6.4 Trial Design/Dosing/Procedures Modifications Permitted Within Protocol Parameters

This is a phase 1 assessment of TAK-831 in healthy subjects. The PK, PD, and safety profiles of the compound are still being elucidated. This protocol is written with some flexibility to accommodate the inherent dynamic nature of phase 1 dose rising trials. Modifications to the dose, dosing regimen, and/or clinical or laboratory procedures currently outlined in Section 6.1 and 6.2 may be required to achieve the trial objectives and to ensure the safety of the trial subjects.

Some alterations from the currently outlined dose and/or dosing regimen may be permitted based on newly available data, but the maximum daily dose/exposure detailed in Section 6.3.2, may not exceed those currently outlined.

- Additional cohorts may be added.
- Repeat of or decrease in the dose of the trial drug administered.
- Entire cohorts may be omitted.
- Increase/decrease in the duration of trial drug administration (eg, number of days), including evaluation of single doses of TAK-831 on QT/QTc intervals based on the established tolerated dose range.
- Adjustment of the dosing interval, for example, divided doses BID to QD, QD to BID, 3 times daily, or vice versa.

- A planned PK data review may be eliminated if agreed to by the sponsor and investigator and if no further increases in total daily dose occur.
- Addition of a PK data review.
- Instructions to take trial drug with or without food or drink may also be modified based on newly available data (ie, food effect is known).
- The planned CSF sample may be eliminated, if agreed to by the sponsor and the investigator.

The PK/PD sampling scheme currently outlined in the protocol may be modified during the trial based on newly available PK or PD data (eg, to obtain data closer to the time of peak plasma concentrations).

Up to an additional 50 mL of blood may be drawn for PK and/or biomarker analyses. This may include repeat samples or modified PK/PD time points based on emerging data. The total blood volume withdrawn from any single subject will not exceed the maximum allowable volume during his/her participation in the entire trial.

The timing of planned procedures for assessment of safety procedures (eg, vital signs, ECG, safety laboratory tests) currently outlined in the protocol may be modified during the trial based on newly available safety, tolerability, PK, or PK/PD data (eg, to obtain data closer to the time of peak plasma concentrations). These changes will not increase the number of trial procedures for a given subject during his/her participation in the entire trial.

Additional laboratory safety tests may be added to blood samples previously drawn to obtain additional safety information (eg, adding creatine kinase to serum chemistry panel that was already drawn).

It is understood that the current trial may employ some or none of the alterations described above. Any alteration made to this protocol to meet the trial objectives must be detailed by the sponsor in a letter to the Trial File and forwarded to the investigator for retention. The letter may be forwarded to the institutional review board (IRB)/independent ethics committee (IEC) at the discretion of the investigator.

#### 6.5 Trial Beginning and End/Completion

# 6.5.1 Definition of Beginning of the Trial

The overall trial begins when the first subject signs the trial informed consent form.

#### 6.5.2 Definition of End of the Trial

The overall trial ends when the last subject completes the last planned or Follow-up Visit/interaction associated with a planned visit (this can be a phone contact), discontinues from the trial, or is lost to follow-up (ie, the investigator is unable to contact the subject); or dosing of future cohorts is stopped based on the dose escalation rules.

# **6.5.3** Definition of Trial Completion

The primary objective of this phase 1 trial is to identify safety and tolerability of multiple rising doses. Therefore, it is possible that not all planned doses to be administered, if this objective is achieved at lower dose levels in this trial. This is not considered an early termination of the trial, but rather an earlier than anticipated achievement of the trial objective(s) or trial completion. Therefore, the definition of trial completion follows the same rules as definition of end of trial (Section 6.5.2) for the dosing group achieving the primary objective.

